#### **7.4.4 Serious Adverse Events—Reporting**

It is the responsibility of the Investigator to report SAEs to the Sponsor (Tufts) within 24 hours of awareness of the event or safety information, whether initial or follow-up, and of the Sponsor to fulfill all SAE reporting requirements to the FDA and to the manufacturer of NEOD001 (Prothena).

1) For expedited reporting of SUSARs, Tufts Medical Center will send the SAE report to Prothena and Novella at the following email addresses:

- a. [[contact]](mailto:[contact])
- b. [[contact]](mailto:[contact])

2.) For annual and ad hoc safety reporting, Tufts Medical Center will send SAE reports only to Prothena

- a. [[contact]](mailto:[contact])

All SAEs must be reported immediately (within 24 hours of awareness) to the Sponsor (Tufts Medical Center). Do **not** delay in the reporting of a suspected SAE in order to obtain additional information. Any additional information, if collected, can be reported to the Sponsor as a follow-up to the initial report. SAEs will be reported using the SAE forms provided as part of the study. Please remember to give details of the subject identification number or other appropriate terminology and ensure the narrative is comprehensive and includes a chronology and assessment of the event.

Reporting of SAEs to the Institutional Review Board/Institutional Ethics Committee (IRB/IEC) will be done in compliance with the standard operating procedures and policies of the IRB/IEC of record and with applicable regulatory requirements. Adequate information must be obtained by the Sponsor or its designee showing that the IRB/IEC was properly and promptly notified as required.

The Investigator is encouraged to discuss any AEs with the Sponsor Medical Monitor for which the issue of seriousness is unclear or questioned. The Medical Monitor for this study is [name] and you may contact him by phone at [contact] and by e-mail at [[contact]](mailto:[contact]).

The reporting period for SAEs is the period from signing of the ICF through 30 days after the last administration of study drug or through the EOS/ETD Visit, whichever is later. SAEs reported to the Investigator outside of this reporting period will be reported to the Sponsor or its designee only if, in the judgment of the Investigator, there is "a reasonable possibility" that the event may have been caused by the product.

All SAEs will continue to be followed until the end of the study or until such events have resolved or the Investigator, in conjunction with the Sponsor or its designee, deems them to be chronic or stable.

#### **7.4.5 Data Safety and Monitoring Committee**

An independent Data Safety Monitoring Committee (DSMC), consisting of at least 2 clinicians and a biostatistician not directly involved with the conduct of the trial, will meet to review specified blinded subject data during the conduct of the study. The purpose of these independent data reviews is to assess the totality of the safety data and provide recommendations for protocol modifications. Tufts Cancer Center Data Safety and Monitoring Board (DSMB) operates as an independent oversight committee and will be used to monitor the trial for the safety of the participants. The DSMB meets quarterly. The sponsor, Tufts Medical Center, will be responsible for providing DSMB committee members with a summary of the study data and all other requested information at least 7 days before the scheduled meeting.

An ad-hoc meeting may be called by the principal investigator, Medical Monitor or by the DSMB chairperson. In the event of an SAE or an emergent safety concern, the principal investigator or his designee will report the event to the IRB and to the DSMB chairperson. The DSMB will meet within 7 days (via conference call or e-mail discussion) following the notification of an unanticipated problem. The structure of the ad hoc meetings will follow that of regular meetings. The DSMB members will vote on recommendations for continuing, modifying, or stopping enrollment in the trial. The chairperson will provide the sponsor with a written report summarizing the recommendations. In addition, the study will be placed on the agenda for the next regular DSMB meeting to review the follow-up actions and reassess risk.

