### **3.4.2 Emergency Unblinding**

The Investigator has the ability to break the blind for a specific subject in the event of an immediate medical emergency wherein knowledge of the subject's treatment (NEOD001 or placebo) must be known in order to provide adequate medical treatment. In these situations, the breaking of the blind must be reported to the Sponsor (Tufts) or its designee within 24 hours. Subjects may continue to receive study treatment with the approval of the medical monitor.

One or two Unblinded Pharmacists or an appropriate designee (henceforth collectively referred to as the Unblinded Pharmacist) will be identified at each site who will be responsible for preparing the study drug; all other study team members must remain blinded to study drug assignment. The Unblinded Pharmacist will obtain the randomization number and treatment assignment information from the IWRS, and will then prepare and reconstitute the study drug, providing it to the Investigator for administration. The Unblinded Pharmacist will maintain the records for drug accountability for audits or inspections.

Any other requests to reveal a subject's treatment must be requested of, and approved in writing by, the Sponsor (Tufts).

In addition, in the event of any safety concern, the Data Safety Monitoring Committee (DSMC) will have the option to unblind the treatment of any subject. In this situation, only the SMC will have access to the unblinded data.

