**The most common side effects seen in ≥ 10% of the NEOD001-001 (Phase 1/2) subjects include:**

- Increased creatinine in blood
- Dizziness
- Cough
- Constipation
- Headache
- Vomiting
- Difficulty breathing (Dyspnea)
- Pain in hands and legs (pain in extremity)
- Back pain
- Muscle spasms
- Rash
- Urinary tract infection

Twenty three subjects were enrolled in the Phase 2 study and 129 subjects were enrolled in the Phase 3 study and received 24 mg/kg NEOD001 or placebo; the patients did not know what they were receiving. In the Phase 2 study, one subject experienced vasovagal syncope (fainting) but recovered from it.

Sixty-eight (52.7%) subjects had at least 1 serious side effect in the Phase 3 study. The serious side effects investigators thought were related to study drug in this blinded study, include the following: anemia and acquired factor VIII deficiency (a rare but potentially life-threatening bleeding disorder); both events resolved. Sinus Tachycardia (increased heart rate), [resolved and the subject remained in the study]. Increased Liver Enzymes event (GGT increased, 3 alkaline phosphatase, and AST increased) was resolved and the syncope (fainting), the subject who experienced fainting remains in the study.

There is always a chance that an unexpected side effect, including death, may happen to people who take this study drug or any drug. Participants vital status including organ function and immune function will be monitored by the study doctor/staff at least monthly during the study. Participants should tell the study

doctor or medical team about any side effects they are having. The study doctor may be able to give medications to help treat the side effects and prevent them from becoming worse. The study doctor may also choose to stop NEOD001 for a short time or reduce its dose to allow the participant to recover from any side effects.

Amyloid can deposit in vital organs, such as your heart, kidney, liver, spleen. The amyloid in organs can cause them to not function as well as they should. Though NEOD001 is being investigated for its potential to stop or even reverse your organ dysfunction, it is possible that it could cause worsening of organ function when the drug targets the amyloid already deposited in organs. Participants organ function will be monitored closely with blood and urine tests and physical examinations throughout the study.

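### Routine safety review is of blinded data, and no by-arm review of organ worsening is planned, although the protocol names it as a possible drug harm

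*Combined protocol and SAP*

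**What the plan says.** Section 7.4.5 sets up a DSMC "consisting of at least 2 clinicians and a biostatistician not directly involved with the conduct of the trial". The committee "will meet to review specified blinded subject data during the conduct of the study". Of its task the section says "The purpose of these independent data reviews is to assess the totality of the safety data". It does not list the data to be reviewed or define blinded, and it gives no by-arm table and no trigger for unblinding.

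The same section describes the cancer center's DSMB, which "operates as an independent oversight committee and will be used to monitor the trial for the safety of the participants". The quarterly schedule belongs to this body. The sponsor supplies it with a summary of study data and whatever else is requested, and its members vote on whether enrollment continues, changes or stops. Whether the summary is by arm is not stated.

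On unblinding, Section 3.4.2 says "in the event of any safety concern, the Data Safety Monitoring Committee (DSMC) will have the option to unblind the treatment of any subject", and that in this situation "only the SMC will have access to the unblinded data". The relation between DSMC, DSMB and SMC is not explained. The table of contents names Section 7.4.5 after a Board, while the section heading names it after a Committee.

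Section 10 says of the drug that "it is possible that it could cause worsening of organ function when the drug targets the amyloid already deposited in organs". Section 7.4.3 treats hematologic and organ progression as efficacy data and not as an AE or SAE term, although a serious event that results from progression is reported under its own diagnosis.

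**The concern.** In patients with persistent renal amyloid, a drug-induced fall in kidney function looks like the disease. A single case seldom tells the two apart, whereas a comparison between randomized arms can. The final analysis will make that comparison (Sections 8.3.2 and 8.4), but nothing in the plan provides for it routinely while patients are being treated.

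The unblinding option depends on a concern arising first. If blinded data show declines at about the rate that members expect from the disease, they have no reason to use it. An eGFR decline without a serious consequence may also stay outside the AE and SAE listings. At stake is the delay: an excess of renal or cardiac worsening on NEOD001 could continue over several quarterly meetings before anyone placed to act on it compared the arms.

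**Working it through.** The plan states no figure on this point, so there is none to reproduce. The one input from the plan is 50 patients per arm (Section 3.3). The documents give no expected rate of organ worsening, so all event counts and rates below are assumptions.

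**1. One overall count, two splits.** Take 20 patients with eGFR decline among 100, an overall rate of 20/100 = 20%. Given 20 events in all, the number k in one arm has probability C(50,k) × C(50,20−k) / C(100,20) when the arms do not differ.

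- 10 v 10: 20% in each arm, two-sided Fisher p = 1.00.
- 5 v 15: 10% v 30%. The p-value is P(k ≤ 5) + P(k ≥ 15) = 0.0114 + 0.0114 = 0.023.

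The overall figure is 20% in both cases, so it cannot distinguish them.

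**2. Could an overall rate still raise the alarm?** It could, if the background rate were known. Suppose the true rates are 10% on placebo and 30% on NEOD001, and use one-sided tests at 0.05.

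- By-arm comparison, 50 per arm: power 0.81.
- Overall count tested against the correct background of 10%: the alarm is raised at 16 or more events in 100, and the chance of reaching it is 0.88.
- Overall count tested against a background wrongly taken as 20%: the alarm is raised at 28 or more, and the chance is 0.03.

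Review of an overall rate is thus as good as the knowledge of the background, and an error of 10 percentage points removes nearly all of its sensitivity. The documents give no background rate. The by-arm comparison does not need one.

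**3. The other routes, side by side.**

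| Route | Section | Compares arms? |
|---|---|---|
| Routine DSMC review | 7.4.5 | Not stated; data are blinded |
| DSMC unblinding | 3.4.2 | Possible, but optional, framed by subject, and after a concern |
| Quarterly DSMB summary | 7.4.5 | Not stated; supplied by the sponsor |
| Laboratory review before each dose | 6.5.1.1 | No; one patient at a time |
| Medical monitor follow-up of eGFR below 30 | 3.5 | No; a large fall can also end above 30 |
| AE and SAE reporting | 7.1, 7.4.3 | No; progression itself is not a term |

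No route provides a routine comparison between arms.

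**The case against.** The strongest reply is that the committee is not confined to blinded data. Section 3.4.2 allows unblinding on any safety concern and for any subject, and sets no statistical threshold. Because the protocol itself warns of organ worsening, a cluster of declines could be concern enough. DSMB members may also request further information and call ad hoc meetings. All of this stands. A reader might infer that the committee sees only blinded data and can never detect an imbalance, and the documents do not support that. They show that the comparison is left to discretion and depends on a prompt that blinded data may not give.

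Second, Section 7.4.5 says blinded, not pooled. Blinded could mean arms masked as A and B, which would show an imbalance though not its direction. That is a fair reading, and step 1 applies only if the arms are combined. If masked arms are meant, the sponsor need only say so and make the codes available to the committee.

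Third, a reader might infer that one committee meets quarterly on blinded data. The text attaches blinded to the DSMC and quarterly to the DSMB, and says neither that they are one body nor that the DSMB summary is blinded.

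Fourth, a by-arm report would not settle the matter early. If the 5 v 15 excess built up evenly, the position with 25 patients per arm would be about 2/25 v 8/25 (p = 0.074) or 3/25 v 7/25 (p = 0.29). The report would let members see the direction and ask further, but would not guarantee nominal significance midway.

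Lastly, monthly laboratory review and the medical monitor make it unlikely that marked declines in individual patients go unnoticed. What could be missed is the difference between arms.

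**Conclusion.** The concern holds as a gap in the monitoring plan: no routine by-arm review of organ worsening is specified, although the protocol names that harm and records organ progression outside the AE and SAE terms. The DSMC's option to unblind and the DSMB's right to request information reduce the gap but do not close it. The first needs a concern to arise, and for the second no unblinded preparer separate from the sponsor is named.

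The size can only be illustrated. On assumed counts, 20/100 overall is compatible with no difference (p = 1.00) and with a threefold excess, 10% v 30% (p = 0.023). This rests on blinded meaning that arms are combined and on members having no firm background rate. It is not evidence that the drug causes such an excess. The change is a low-cost improvement that should be made; the point does not affect the primary analysis or the sample size.

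**What to change.** In Section 7.4.5, replace the blinded review with a closed report by treatment group, coded A and B and decodable by the committee on request, at each quarterly meeting. It should cover AEs, SAEs, deaths, eGFR decline, and renal and cardiac progression. The independent biostatistician already on the committee prepares it. The sponsor, investigators and medical monitor stay blinded.

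Reconcile DSMC, DSMB and SMC in Sections 3.4.2 and 7.4.5, so that one named body receives the report, meets quarterly and holds the right to unblind.

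Cost: wording in two sections, and a controlled transfer of the randomization list and the safety data. The data transfer needs its own provision, because Section 12.4 gives access to all sites' data to the sponsor alone. One more person would hold the codes, and the member who prepares the report would also help to judge it. Visits, dosing and the primary analysis do not change.

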### **8 STATISTICAL METHODS AND CONSIDERATIONS**

#### **8.1 Analysis Populations**

Primary efficacy analysis is based on patients who are randomized and receive treatment for 12 months with NEOD001 or placebo.

Analysis of secondary time-to-event and also safety endpoints will be based on intention-to-treat. All patients randomized and treated with NEOD001 or placebo will be included.

The following subject populations will be evaluated and used for presentation and analysis of the data:

1. The Intent-to-Treat Population will include all randomized subjects who receive any amount of study drug (NEOD001 or placebo). Treatment assignment will be based on the randomized treatment.
2. The Safety Population will include all subjects who received any amount of study drug (NEOD001 or placebo). The Safety Population will be the primary population used for safety analyses. Treatment assignment will be based on the treatment actually received. For example, in the event of randomization, dispensing, or treatment errors, subjects will be included in the treatment group based on the treatment that was received.

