## 4.3 Early Treatment Discontinuation

If the subject discontinues study drug prior to the initial EOS visit, the subject should return for an ETD Visit 30 ( $\pm 5$ ) days after their final administration of study drug as per Section 6.2. If a subject fails to return for the scheduled visit, a documented effort must be made to determine the reason. If the subject cannot be reached by telephone after 2 attempts, a certified letter will be sent to the subject (or the subject's legally authorized representative, if appropriate) requesting contact with the Investigator. This letter will be submitted to the IRB for review prior to use. This information will be recorded in the study records.

If the subject discontinues study drug prior to initial EOS visit, but is willing to continue to participate in study visits, continue to collect data through the ETD Visit (i.e., 30 [ $\pm 5$ ] days after their final administration of study drug). Following the ETD Visit, subsequent clinic evaluations will be standard-of-care visits with testing as clinically warranted, usually at a minimum of every 3 months. Testing in this circumstance can be performed at a distance. Every effort should be made for the subject to return to the clinic at the month 12 time point for completion of all of the initial EOS visit assessments.

Reasons for early discontinuation from study drug treatment may include, but are not limited to:

- Hematologic progression requiring immediate initiation of chemotherapy; the chemotherapy regimen should be documented on the appropriate case report form.
- Need for organ transplant or major surgery.
- Occurrence of an AE or clinically significant laboratory abnormality that, in the opinion of the Investigator, warrants the subject's permanent discontinuation from study drug treatment; the Medical Monitor ([name]) should be notified as soon as possible of any discontinuation of study drug due to an AE.
- Suspected or confirmed pregnancy or nursing during study treatment period. Female subjects whose pregnancy test is positive at the ETD visit must be followed to term or until termination of the pregnancy.

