#### **8.5. Determination of Sample Size**

This stratified randomized double-blind phase 2b study has as its primary efficacy end-point the confirmed renal response rate at 13 months after initiating therapy and is designed to detect an absolute increase in the renal response rate of 30% (from 25% in those receiving placebo to 55% in those receiving NEOD001). For the primary efficacy endpoint, the assumed true rates for NEOD001 vs placebo are 55% and 25%, respectively. Based on a chi-squared statistic to evaluate the null hypothesis at the alpha=0.05 level of significance, and assuming an 18% drop-out rate for hematologic progression requiring chemotherapy, a total sample size of 82 subjects (41 in the placebo group, 41 in the NEOD001 group) will enable us to reject the null hypothesis that the response rates for subjects receiving NEOD001 and placebo are equal with probability (power) 0.8. With 50 patients receiving placebo and 50 patients receiving NEOD001, we expect to have at least 41 evaluable patients in each group.

Of note, we are estimating the renal response rate over time in the arm not receiving NEOD001. In the relapsed setting, patients receiving lenalidomide and dexamethasone had an 18% renal response rate at 6 and 12 months; an additional 18% responded by 18 months. In relapsed patients receiving cyclophosphamide, lenalidomide and dexamethasone, 19% had renal responses, while in a phase 1/2 trial in relapsed patients (N=70) treated with bortezomib, 29% had a renal response. In the initial therapy setting, patients with renal involvement who received cyclophosphamide, bortezomib and dexamethasone (CyBorD) had a 25% renal response rate. Post-ASCT with bortezomib-based consolidation, while 50% of renal patients respond by the end of the first year, an additional 20% of renal patients respond in the second year post-ASCT. While we do not know the mix of patients who will be screened and enrolled in this trial, it is reasonable to assume that one third will be post-SCT, one third post initial and one third post second-line therapy. Allowing for a 6 month interval after chemotherapy and a 12 month interval after SCT, the weighted average of the renal response rates in these groups is 22.3%. We have chosen a higher estimate (25%) as the confirmed renal response rate in this study in patients receiving placebo.

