## **8.6 Handling of Dropouts and Missing Data**

Subjects who discontinue during the study period with ETD visits will be included in intent-to-treat but not the primary endpoint analyses. The number of such subjects will be noted in the summary table of outcomes. Analyses excluding these subjects will also be performed and described. Observed data will be included in listings and summary tables. There will be no imputation of missing data.

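### The primary analysis keeps only subjects who complete 12 months of study drug, so early discontinuers drop out of the denominator instead of counting as non-responders

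*Combined protocol and SAP*

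**What the plan says.** Section 8.1 (Analysis Populations) sets the primary analysis: "Primary efficacy analysis is based on patients who are randomized and receive treatment for 12 months with NEOD001 or placebo". It then assigns intention-to-treat elsewhere: "Analysis of secondary time-to-event and also safety endpoints will be based on intention-to-treat". The same section defines an Intent-to-Treat population of randomised subjects who received any study drug, analysed by assigned arm.

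Section 8.6 (Handling of Dropouts and Missing Data) agrees: "Subjects who discontinue during the study period with ETD visits will be included in intent-to-treat but not the primary endpoint analyses". It adds "Analyses excluding these subjects will also be performed and described" and "There will be no imputation of missing data".

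Section 8.5 builds the loss into the sample size, "assuming an 18% drop-out rate for hematologic progression requiring chemotherapy", and concludes that with 50 per arm "we expect to have at least 41 evaluable patients in each group".

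Section 4.3 lists reasons for stopping drug, including "Hematologic progression requiring immediate initiation of chemotherapy" and adverse events or laboratory abnormalities. It asks discontinuers to come back at month 12 for the initial EOS assessments. Section 1.1 requires a confirmed response to be present at both month 12 and month 13.

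**The concern.** Completing 12 months of drug is a post-randomisation outcome. Once the analysis conditions on it, randomisation no longer guarantees that the two groups are comparable.

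The excluded subjects are unlikely to be a random subset. Section 8.5 attributes the whole budgeted loss to haematologic progression, and Section 4.3 adds adverse events. Section 10 says that worsening organ function may lead to study drug not being given, while renal progression rules out a renal response. A likely non-responder can therefore leave the denominator. A subject who dies before month 12 is also excluded by implication, although the analysis text does not mention death.

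Section 8.6 implies that some analysis includes the discontinuers. It gives no rule for scoring their confirmed response and gives that analysis no primary status. The month-12 return visit does not repair this, because no month-13 confirmation is requested for these subjects and Section 8.1 would exclude them anyway. If losses are unequal between arms, the primary test has no protection.

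**Working it through.** **Inputs from the documents.** Response rates 55% (NEOD001) and 25% (placebo), two-sided alpha 0.05, power 0.80, drop-out 18%, 41 evaluable and 50 randomised per arm (Sections 8.3.1 and 8.5).

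**Assumptions.** Drop-out by arm is not given, so the splits below are assumed. All calculations use the unstratified Pearson chi-squared test rather than the planned stratified Mantel-Haenszel test. Rejection rates are exact binomial enumerations unless marked approximate.

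**Step 1. The plan's own figure.** With a pooled rate of 0.40:

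n = [1.960·√(2·0.40·0.60) + 0.8416·√(0.25·0.75 + 0.55·0.45)]² / 0.30² = 40.7, so 41 per arm.

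Power at 41 per arm is 80.3% (approximate) or 81.7% (exact), and 41/(1 − 0.18) = 50. The stated sample size reproduces, so the problem lies in the analysis set and not in the arithmetic.

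**Step 2. No drug effect, every drop-out a non-responder in both arms.** The completer rate equals the rate among all dosed subjects divided by (1 − drop-out).

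| Drop-out (arm A / arm B) | Response, all dosed | Completers, A / B | Completer rate, A / B | Completer test rejects | All 50 per arm rejects |
|---|---|---|---|---|---|
| 18% / 18% | 25% | 41 / 41 | 30.5% / 30.5% | 4.9% | 5.1% |
| 30% / 18% | 25% | 35 / 41 | 35.7% / 30.5% | 7.8% | 5.1% |
| 26% / 10% | 20.5% | 37 / 45 | 27.7% / 22.8% | 8.7% | 5.2% |

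In the last two rows most rejections favour the arm that lost more subjects (7.1 of the 7.8 points and 8.0 of the 8.7). With smaller gaps and 20.5% of all dosed responding, the completer test rejects at 5.1% (20% vs 16%) and 6.1% (22% vs 14%).

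**Step 3. No drug effect, drop-out unrelated to response.** With 25% response in both arms, the completer test rejects at 5.1% (41 vs 41) and 5.5% (35 vs 41).

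**Step 4. A true effect.** Take 45.1% vs 20.5% among all dosed, which is 55% and 25% multiplied by 0.82, with drop-outs as non-responders.

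- Placebo drop-out 30%, NEOD001 18%: completer rates are 29.3% (n = 35) and 55.0% (n = 41), and completer power is 62%.
- Split reversed: completer rates are 25.0% (n = 41) and 64.4% (n = 35), and completer power is 95%.
- All 50 per arm: 76% in both cases.

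**Step 5. What one data set could look like.** Suppose 11/45 placebo and 20/37 NEOD001 completers respond: p = 0.006. The same responders over everyone dosed, 11/50 vs 20/50, give p = 0.052.

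**Step 6. Power after the fix, 50 per arm.** If 55% and 25% are completer rates, the rates become 45.1% and 20.5%, a difference of 24.6 points. Power is 75.3% (approximate) or 75.6% (exact). Sample size for 80% power, with pooled rate 0.328:

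n = [1.960·√(2·0.328·0.672) + 0.8416·√(0.205·0.795 + 0.451·0.549)]² / 0.246² = 55.98, so 56 per arm.

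If 55% and 25% describe all dosed subjects, power is 87.6% (approximate) or 88.1% (exact). Over equal drop-out of 10% to 25%, with completer rates fixed, approximate power runs from 81% to 70%, and 80% power needs 49 to 64 per arm.

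**The case against.** There is a serious case for the plan as written.

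- **Balanced losses are plausible.** The only cause budgeted is haematologic progression. Section 1.3 describes an antibody against misfolded light chain and amyloid deposits, with no action on the plasma-cell clone. The trial is double-blind, and Section 1.3.1 reports no phase 1/2 patient stopping for a drug-related adverse event. This lowers the risk. It does not remove it, since Section 4.3 lists other reasons and Section 10 accepts that the drug itself could worsen organ function.
- **The inflation needs wide gaps.** The 7.8% and 8.7% figures assume gaps of 12 and 16 points and no response in any drop-out. Smaller gaps give 5.1% to 6.1%. This stands, and the figures should be read as illustrations.
- **The fix changes the question.** If drop-out is unrelated to response but unequal, scoring drop-outs as non-responders rejects at 7.0% (30% vs 18%) and 8.0% (26% vs 10%) when 25% of completers respond in both arms. These are not false positives for the redefined endpoint, because the composite rates then really differ (17.5% vs 20.5%, and 18.5% vs 22.5%). It is right, however, that stopping treatment becomes part of the outcome, and the plan should say so.
- **An on-treatment question is recognisable.** The objective concerns patients who do not need chemotherapy, and the sizing is consistent with a completer set. But a need for chemotherapy that arises after randomisation is not a baseline characteristic and cannot define the compared groups without risk of bias.
- **Observed month-12 data could be used instead.** Scoring every discontinuer as a non-responder discards a response seen at the return visit. Using such data is a legitimate alternative, but it would need a confirmatory visit that Section 4.3 does not request.

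**Conclusion.** The concern holds. Sections 8.1 and 8.6 both confine the single primary test to 12-month completers, Section 8.5 sizes the trial on that basis, and nothing in the plan scores discontinuers or gives primary status to an analysis that includes them.

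The bias is possible, not demonstrated. Under the assumed unequal splits, two-sided error rises from about 5% to between 7.8% and 8.7%, and completer power moves to 62% or 95% depending on which arm loses more. If drop-out is unrelated to response, error stays near 5%. Equal drop-out rates are not a full safeguard either, because the reasons for stopping could still differ by arm.

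This must be fixed: it concerns the primary test and about 18 of 100 subjects, and a change made after unblinding would carry little credibility.

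**What to change.** 1. In Sections 8.1, 8.3.1 and 8.6, make the existing Intent-to-Treat population (randomised and dosed, by assigned arm) primary for confirmed renal response.
2. Count as a non-responder any subject who dies, discontinues early, starts chemotherapy before the confirmatory EOS visit, or lacks either EOS renal assessment. State that this composite is the intended estimand, and amend the no-imputation sentence in Section 8.6 to match.
3. Keep the 12-month completer analysis as supportive.
4. Report by arm the number randomised but not dosed, since this population omits them and Section 4.5 allows their replacement.
5. In Section 8.5, state which subjects the 55% and 25% describe. As written they apply to 41 evaluable per arm, so power for 50 per arm should be given as about 75%. About 88% applies only if they are rates among all dosed subjects.

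The cost is protocol and SAP wording, with no change to visits or enrolment. The downside is that stated power may fall from 80% to about 75%. Holding 80% at 45.1% vs 20.5% would take 56 per arm (112 in total) instead of 50.
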